7.3. Vital Signs

Vital signs (systolic and diastolic blood pressure [mmHg], pulse [beats/min]) at each visit, and change from baseline at each visit will be summarized for the Safety Analysis Set using descriptive statistics (n, mean, SD, median, Q1, Q3, minimum, and maximum) by treatment group. The baseline value will be defined as the last available value collected on or prior to the date/time of first dose of study drug. Change from baseline to a postbaseline visit will be defined as the postbaseline value minus the baseline value.

In the case of multiple values in an analysis window, data will be selected for analysis as described in Section 3.7.3 (Selection of Data in the Event of Multiple Records in a Window). No inferential statistics will be generated.

A by-subject listing of vital signs (systolic and diastolic blood pressure [mmHg], pulse [beats/min], respiration [breaths/min], and body temperature [$^{\circ}$ C]) will be provided by subject ID number and visit in chronological order.

7.4. Body Weight, Height and BMI

An age- and sex-specific percentile will be derived for each weight, height and BMI measurement according to the downloadable SAS program available on the Centers for Disease Control (CDC) website using the year 2000 growth charts. Methods and SAS program published on the following CDC website will be applied to calculate the percentile {[Centers for Disease Control and Prevention \(CDC\) 2016a](#), [Centers for Disease Control and Prevention \(CDC\) 2016b](#)}.

Body weight, height, BMI and percentiles for body weight, height, BMI at each visit, and change from baseline at each visit will be summarized for the Safety Analysis Set using descriptive statistics (n, mean, SD, median, Q1, Q3, minimum, and maximum) by treatment group.

In the case of multiple values in an analysis window, data will be selected for analysis as described in Section 3.7.3 (Selection of Data in the Event of Multiple Records in a Window). No inferential statistics will be generated.

A by-subject listing of body weight, weight percentile, height, height percentile, BMI and BMI percentile will be provided by subject ID number and visit in chronological order.

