### 9.1.3. Secondary Endpoints

For the PK Lead-in Phase, the secondary endpoints include antiviral activity measurements, including assessment of HCV RNA. AEs leading to permanent discontinuation of study drug(s) will be evaluated as a secondary safety endpoint.

For Treatment Phase, secondary efficacy endpoints include SVR4, SVR24, breakthrough and relapse. Additional efficacy evaluations may include HCV RNA change from Day 1; ALT normalization; viral kinetic parameters, and palatability of SOF oral granules. Secondary safety endpoints of growth and development measurements will be assessed (e.g. height, weight, and Tanner Stage Assessment).

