1.1. Study Objectives

The primary objectives of this study are as follows:

- The primary objective of the pharmacokinetics (PK) Lead-in Phase of this study is to evaluate the steady state PK and confirm the dose of sofosbuvir (SOF) in hepatitis C virus (HCV)-infected pediatric subjects.
- The primary objective of the Treatment Phase of this study is to evaluate the safety and tolerability of SOF + ribavirin (RBV) for 12 or 24 weeks in HCV-infected pediatric subjects with genotype 2 or 3, respectively

The secondary objectives of this study are as follows:

- The secondary objective of the PK Lead-in Phase of this study is to evaluate the safety and tolerability of 7 days of dosing of SOF + RBV in HCV-infected pediatric subjects.
- The secondary objectives of the Treatment Phase of this study are:
 - To determine the antiviral efficacy of SOF + RBV treatment in genotypes 2 and 3 HCV-infected subjects separately, as assessed by the proportion of subjects with sustained viral response 12 weeks after discontinuation of therapy (SVR12)
 - To determine the antiviral efficacy of SOF + RBV treatment in genotypes 2 and 3 HCV-infected subjects separately, as assessed by the proportion of subjects with sustained viral response 4 and 24 weeks after discontinuation of therapy (SVR4 and SVR24)
 - To evaluate the kinetics of circulating HCV RNA during treatment and after treatment discontinuation
 - To evaluate the emergence of viral resistance to SOF during treatment and after treatment discontinuation
 - To evaluate the palatability of SOF oral granules at Day 1, as applicable
 - To evaluate the effect of growth and development on pediatric subjects during and after treatment

The exploratory study objective is as follows:

- PPD

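### The only age- and sex-adjusted summary of weight, height and BMI is on the percentile scale; adding change in z-score would stop losses in shorter or lighter children being compressed.

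*SAP*

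**What the plan says.** Growth is part of a secondary objective of the Treatment Phase; SAP 1.1 words it as "To evaluate the effect of growth and development on pediatric subjects during and after treatment". Protocol 9.1.3 makes it a safety endpoint: "Secondary safety endpoints of growth and development measurements will be assessed". The protocol does not say on which scale.

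SAP 7.4 supplies the scale: "An age- and sex-specific percentile will be derived for each weight, height and BMI measurement", using the year 2000 CDC growth charts. It then plans this: "Body weight, height, BMI and percentiles for body weight, height, BMI at each visit, and change from baseline at each visit will be summarized". The summary is made "using descriptive statistics (n, mean, SD, median, Q1, Q3, minimum, and maximum) by treatment group", and the section adds: "No inferential statistics will be generated". For individual data, "A by-subject listing of body weight, weight percentile, height, height percentile, BMI and BMI percentile will be provided".

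Protocol 6.6.5 also calls for raw weight and height differences from Day 1 to end of treatment and to post-treatment Weeks 12 and 24. Neither document plans a z-score for weight, height or BMI. The term appears only in the bone mineral rows of the grading scale in Protocol Appendix 3.

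**The concern.** The trial has one arm and no reference therapy. Subjects are aged 3 to under 18 and are followed for 12 or 24 weeks of treatment plus 24 weeks afterwards. Over that time raw height and weight change mixes ordinary growth with any treatment effect, and ordinary growth differs by age and sex. For weight, height and BMI, the growth chart is therefore the plan's only means of separating the two.

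The chart position is carried forward only as a percentile. Equal losses in SD units give unequal changes in percentile, depending on where the child starts: largest at the median and small in either tail. A mean percentile change is thus a weighted average in which children far from the median count for little. Protocol 1.1 reports debate about whether peginterferon and ribavirin slow growth, and every subject here receives ribavirin. The scale of the one adjusted summary therefore affects what a reader can see.

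**Working it through.** The documents give no numerical figure for growth, so there is none to reproduce. The check concerns the size of the compression.

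**Inputs.** From SAP 7.4: the metric is an age- and sex-specific percentile, and change from baseline is summarised. Assumed, because the documents do not give them: percentile = 100 × Φ(z), with Φ the standard normal distribution function; starting positions z0; and a loss of d SD.

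**Formula.** Fall in percentile points = 100 × [Φ(z0) − Φ(z0 − d)]. Ratio = fall from the median ÷ fall from z0.

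**Loss of d = 0.25 SD.**

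- From z0 = 0: 50.000 − 40.129 = 9.871 points.
- From z0 = −1: 15.866 − 10.565 = 5.301 points; ratio 9.871 ÷ 5.301 = 1.9.
- From z0 = −2: 2.275 − 1.222 = 1.053 points; ratio 9.871 ÷ 1.053 = 9.4.

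**Sensitivity to starting position (d = 0.25 SD).**

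| Starting position | Fall (points) | Ratio to median |
|---|---|---|
| −0.5 SD | 8.19 | 1.2 |
| −1 SD | 5.30 | 1.9 |
| 10th percentile | 3.72 | 2.7 |
| 5th percentile | 2.09 | 4.7 |
| 3rd percentile | 1.35 | 7.3 |
| −2 SD | 1.05 | 9.4 |
| −2.5 SD | 0.32 | 30.6 |

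**Sensitivity to size of loss (z0 = −2 SD).** The ratio is 7.5 for 0.01 SD, 8.2 for 0.1, 9.0 for 0.2, 9.8 for 0.3 and 11.6 for 0.5.

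**Effect on a group mean.** In a constructed example, four children at −2 SD each lose 0.25 SD and one child at the median gains 0.25 SD.

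- Mean percentile change = (9.871 − 4 × 1.053) ÷ 5 = +1.1 points.
- Mean z change = (0.25 − 4 × 0.25) ÷ 5 = −0.15 SD.

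The signs differ. The mix of children is extreme and chosen to show the mechanism; it is not a forecast for this trial.

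**A loss shared by everyone.** If baseline z is normal with mean m and SD 1, the mean percentile is 100 × Φ(m/√2).

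- m = 0, uniform loss of 0.25 SD: 100 × [Φ(0) − Φ(−0.177)] = 7.0 points.
- m = −0.5: 6.4 points.
- m = −1: 5.1 points.

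**On the z-score scale.** A loss of d counts as d for every child, so the ratio is 1.0 at any starting position.

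**The case against.** The strongest reply is that this is largely a choice of presentation. SAP 7.4 also summarises raw weight, height and BMI and their changes; it gives medians, quartiles and extremes as well as means; and it lists every subject's raw values and percentiles. Mid-parental height, bone age and Tanner stage are covered in SAP 7.5 to 7.7. No test or decision rule uses the percentile, and z can be recovered from it. A uniform 0.25 SD loss in a cohort that resembles the reference would still move the mean percentile by about 7 points.

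Most of this stands, and it limits the point. What remains is that the raw changes are not adjusted for age and sex, the median and quartiles of percentile change are on the same compressed scale, and a reader of the listing would have to back-transform each record.

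Three stronger readings are tempting, and the documents support none of them.

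- A reader might infer that a short child's loss always counts about nine times less. That figure needs a start near −2 SD and a loss of about 0.2 to 0.25 SD. The documents define neither a short child nor a size of loss, and at −1 SD the ratio is about 2.
- A reader might infer that the metric fails the children at highest risk. Neither document links low baseline stature to greater risk, and Protocol 1.1 speaks of peginterferon together with ribavirin, whereas this regimen contains no peginterferon.
- A reader might infer that the plan would miss a growth effect. The documents give no baseline height distribution from which to show this, and the 7-point calculation argues against it for a loss shared by the whole group.

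**Conclusion.** The point holds as an improvement to the metric. For weight, height and BMI the plan's only age- and sex-adjusted summary is the percentile, which under-weights losses in shorter or lighter children. For a 0.25 SD loss the fall is 9.9 points from the median, 5.3 from −1 SD and 1.1 from −2 SD. These sizes rest on treating the percentile as the normal distribution function of z and on starting points and a loss chosen for illustration. The direction is the same at every below-median start examined. The consequence is modest: growth here is descriptive, unadjusted values are also reported, and a loss spread across the group would remain visible.

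**What to change.** In SAP 7.4:

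- Derive age- and sex-specific z-scores for weight, height and BMI from the same CDC 2000 reference (z = Φ⁻¹(percentile ÷ 100), using unrounded percentiles).
- Summarise the z-score and its change from baseline at each visit by treatment group, with the descriptive statistics the section already lists. A confidence interval for mean change is optional, since the section plans no inference.
- Add the z-scores to the by-subject listing.
- Keep the percentiles and raw values as planned.

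The cost is one derived variable per measure, a few extra table rows and extra listing columns. No new data or visits are needed.

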7.5. Mid-Parental Height Assessment

The calculation of mid-parental height has been a standard procedure for assessing individual child's future adult height since it was first described by Tanner {Tanner 1970}. Mid-parental height was calculated as the average of father's and mother's height. For boys, calculate the sex-adjusted mid-parental height by adding 2.5 inch or 6.5 cm from the mean of the parents' heights. For girls, subtract 2.5 inch or 6.5 cm from the mean of the parents' heights. If any one of parents' heights is missing, the calculation will be excluded.

A by-subject listing of parents' heights and derived mid-parental height will be provided by subject ID number in ascending order.

7.6. Bone Age Assessment

A single X-ray of the left wrist, hand, and fingers will be performed at Day 1 Visit and post-treatment Week 24. Local radiologist will determine the bone age from x-ray.

Bone age at baseline visit, FU-24 visit and change from baseline visit will be summarized for the Safety Analysis Set using descriptive statistics (n, mean, SD, median, Q1, Q3, minimum, and maximum) by treatment group.

A by-subject listing of bone age will be provided by subject ID number in ascending order and visit in chronological order.

7.7. Tanner Pubertal Stage Assessment

The Tanner stages will be used to evaluate the onset and progression of pubertal changes. Females will be rated for pubic hair growth and breast development, and males will be rated for pubic hair growth and genitalia development. The Tanner stages (Pubic Hair and Breasts for female; Pubic Hair and Genitalia for male) at EOT, FU-12 and FU-24 visit will be summarized by baseline Tanner stages using frequency count and percentage by sex overall and within each treatment group.

7.8. Pediatric Quality of Life (PedsQL™ SF-15) Questionnaires, Including Neuropsychiatric Examination by Emotional Function Domain

The PedsQL™ Pediatric Quality of Life Inventory V4.0 Short Form (SF15) will be completed at Day 1, EOT (Week 12 for genotype 2 subjects, Week 24 for genotype 3 subjects, or at Early Termination, if applicable), 12-Week Post-Treatment, and 24-Week Post-Treatment visits. Each survey accompanied by the respective parent proxy survey will be administered to the subject and their parent/legal guardian (with the exception of the Toddlers Report which will only be completed by the parent/guardian) for the current age group at the time of survey administration.

The transformed scale scores (0 to 100 scale) at baseline, EOT (Week 12 for genotype 2 subjects, Week 24 for genotype 3 subjects, or at Early Termination, if applicable), 12-Week Post-Treatment, and 24-Week Post-Treatment visits and change from baseline, change from EOT to posttreatment will be presented for each of the 4 domains of the SF-15 (physical functioning, emotional functioning, social functioning, and school functioning), and the Total Score. Scoring of the SF15 scales will be performed as described in Scaling and Scoring of the Pediatric Quality of Life Inventory™ (PedsQL™) by James W. Varni. A Wilcoxon signed rank test will be used to explore within treatment group changes in status from baseline to EOT (Week 12 for genotype 2 subjects, Week 24 for genotype 3 subjects, or at Early Termination, if applicable), and from EOT to each of the posttreatment time points. Results (p-values) will be presented, but should be interpreted with caution as multiple endpoints are being tested, and the study has not been powered to test these exploratory endpoints. Plot of the mean \pm SD of change from baseline in SF15 summary scores will be presented.

7.9. Prior and Concomitant Medications

Medications collected at screening and during the study will be coded using the current version of the World Health Organization (WHO) Drug dictionary. The medications will be categorized as prior or concomitant using the following definitions:

- Prior medications: any medications taken and stopped prior to or on the date of first study drug administration
- Concomitant medications: any medications taken after the date of first study drug administration and up to the last dosing date of study drug

Concomitant medications will be summarized by preferred name using the number and percentage of subjects for each treatment group. A subject reporting the same medication more than once will be counted only once when calculating the number and percentage of subjects who received that medication. The summary of concomitant medications will be ordered by preferred term in descending frequency. For drugs with the same frequency, sorting will be done alphabetically.

Summaries will be based on the Safety Analysis Set. No inferential statistics will be generated.

For purposes of analysis, any medication with a stop date that is on or prior to the initial study drug dosing date or a start date that is after the last study drug dosing date will be excluded from a concomitant medication summary. If a partial stop date is entered, any medication with the month and year (if day is missing) or year (if day and month are missing) prior to the initial study drug dosing date will be excluded from the concomitant medication summary. If a partial start date is entered, then any medication with the month and year (if day is missing) or year (if day and month are missing) after the study drug stop date will be excluded from the concomitant medication summary. Medications with completely missing dates will be included in the concomitant medication summary.

A summary of prior medications will not be provided.

All prior and concomitant medications (other than per-protocol study drugs) will be provided in a by-subject listing sorted by subject ID number and administration date in chronological order.

7.10. Other Safety Measures

A data listing will be provided for subjects who become pregnant during the study.

7.11. Changes From Protocol-Specified Safety Analyses

There are no deviations from the protocol-specified safety analyses.

8. PHARMACOKINETIC ANALYSES

8.1. PK Analysis in PK Lead-in Phase (Intensive PK Analysis)

Intensive PK Analysis will be performed using PK Lead-in Phase Intensive PK Analysis Set. Concentrations of SOF and GS-331007 from subjects in the PK lead-in Phase over sampling time will be listed and summarized using descriptive statistics (n, arithmetic mean, geometric mean and its 95% confidence interval, coefficient of variation [%CV], SD, median, Q1, Q3, minimum, and maximum) by nominal time and cohort. For Cohorts 1 and 2, plasma samples will be collected for PK analyses following dosing of study drugs on Day 7 at the following time points: 0 (predose), 0.5, 1, 2, 3, 4, 8, and 12 hours postdose. For Cohort 3, plasma samples for PK analyses will be collected at the following time points: 0 (predose), 2, 4, 8, and 12 hours postdose. PK parameters from subjects in the PK lead-in Phase will be summarized (e.g; AUC_{τ} , AUC_{last} , C_{max} , T_{max} , C_{last} , T_{last} , C_{τ} , $T_{1/2}$, volume of distribution and clearance, as appropriate) by cohort.

To confirm the appropriateness of SOF dose for each age group, PK parameters for GS-331007 will be compared between each age group from this study and the SOF NDA patient population (which includes population-PK derived PK exposure data from adult phase 2 and 3 studies) by carrying out an analysis of variance (ANOVA) for log-transformed AUC_{τ} of GS-331007 as the primary endpoint and C_{max} of GS-331007 as a secondary endpoint. Geometric Mean Ratio and its 90% confidence interval will be provided.

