##### 3.1.1. PK Lead-in

The PK Lead-in Phase will evaluate and/or confirm the age appropriate SOF dose by analyzing PK, safety, and antiviral activity of SOF + RBV through 7 days of dosing for each cohort. Children aged 3 to < 6 years, children aged 6 to < 12 years, and adolescents aged 12 to < 18 years with GT-2 or GT-3 HCV infection and evidence of HCV RNA  $\geq$  1000 IU/mL at study entry will be evaluated. Subjects must be treatment naïve to participate in the PK Lead-in Phase. Three cohorts of up to 10 subjects each will be sequentially enrolled:

- Cohort 1: 12 to < 18 years old weighing  $\geq$  45kg
- Cohort 2: 6 to < 12 years old weighing  $\geq$  17kg and < 45 kg
- Cohort 3: 3 to < 6 years old

The study will start with Cohort 1. Subjects will receive SOF (400 mg adult tablet or 4 x 100 mg tablets if determined necessary based on SOF swallowability assessment) + RBV for 7 days with intensive PK conducted on Day 7.

Once Cohort 2 is opened, subjects will receive SOF 200 mg (4 x 50 mg capsules containing granules if determined necessary based on SOF swallowability assessment) + RBV for 7 days with intensive PK conducted on Day 7. Subjects who weigh outside of the  $\geq$  17kg and < 45 kg range will be excluded.

Once Cohort 3 is opened, subjects weighing  $\geq$ 17 kg will receive 200 mg SOF (4 x 50 mg capsules containing granules) + RBV for 7 days with intensive PK conducted on Day 7. Cohort 3 subjects weighing <17 kg will receive 150 mg SOF (3 X 50mg capsules containing granules) + RBV for 7 days with intensive PK conducted on Day 7.

Subjects enrolled in the PK Lead-in of each cohort (Cohorts 1, 2 and 3) will immediately enroll in the Treatment Phase as they complete Day 7 of PK Lead-in. They will continue dosing with SOF + RBV with no interruption of study drug administration. Subjects rolling over from the PK Lead-in Phase will not be required to perform the screening, Day 1 or Week 1 visit of the Treatment Phase.

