### **9.4. Pharmacokinetic Analysis**

PK analysis will be performed for PK Lead-in using the intensive PK analysis set. The concentration data of SOF and metabolites (GS-566500 and GS-331007) over sampling time will be listed and summarized by nominal time and cohort. Pharmacokinetic parameters (e.g.,  $AUC_{\tau}$ ,  $AUC_{last}$ ,  $C_{max}$ ,  $T_{max}$ ,  $C_{last}$ ,  $T_{last}$ ,  $C_{\tau}$ ,  $\lambda_z$ ,  $CL/F$ ,  $V_z/F$  and  $t_{1/2}$ ) will be listed and

summarized for SOF and metabolites (as applicable) using descriptive statistics (e.g., sample size, arithmetic mean, geometric mean and its 95% confidence interval, coefficient of variation %, standard deviation, median, Q1, Q3, minimum, and maximum) by cohort and overall. Plasma concentrations over time will be plotted in semilogarithmic and linear formats as mean  $\pm$  standard deviation, and median (Q1, Q3).

To evaluate the exposures of GS-331007 achieved in pediatric subjects of this study are similar to the exposures observed in adult subjects, GS-331007 exposure data from this study will be compared to the integrated adult data by carrying out an analysis of variance (ANOVA) for log-transformed  $AUC_{\tau}$  of GS-331007 as the primary endpoint while  $C_{\max}$  of GS-331007 as secondary endpoints. The 90% confidence intervals will be constructed for the ratio of geometric means of each PK parameters. The equivalence boundary is set as 50% to 200%. Individual patient management will be performed by maintaining exposures comparable to adults.  $AUC_{\tau}$  less than the 2.5th percentile of adult values may require dose adjustment as appropriate.

The effect of age and SOF dose on PK (SOF and GS-331007) will be assessed.

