3.2. Subject Grouping

For analyses based on the All Enrolled Analysis Set or FAS, subjects will be grouped according to the treatment to which they were enrolled. For analyses based on the Safety Analysis Set, subjects will be grouped according to the actual treatment received. The actual treatment received is defined as the enrolled treatment except for subjects who received treatment that differs from the enrolled treatment for the entire treatment duration. In this case, the actual treatment received is defined as the treatment received for the entire treatment duration.

Specifically, efficacy and safety analyses will be performed according to age group and HCV genotype in the following treatment groups:

Table 3-1. Treatment Groups

12 to < 18 Years Old SOF(400mg)+RBV		3 to < 12 Years Old SOF(200mg or 150mg)+RBV	
GT-2 12 Weeks (N =)	GT-3 24 Weeks (N =)	GT-2 12 Weeks (N =)	GT-3 24 Weeks (N =)
6 to < 12 Years Old SOF(200mg)+RBV		3 to < 6 Years Old SOF(200mg or 150mg)+RBV	
GT-2 12 Weeks (N =)	GT-3 24 Weeks (N =)	GT-2 12 Weeks (N =)	GT-3 24 Weeks (N =)

GT = genotype

Subjects in the 3 to < 6 years of age group will have additional selected efficacy and safety analyses performed according to baseline weight and HCV genotype in the following subgroups:

Table 3-2. Subgroups for Selected Analyses in 3 to < 6 years of Age

3 to < 6 Years Old			
GT-2 12 Weeks		GT-3 24 Weeks	
< 17 kg SOF(150mg)+RBV (N =)	>= 17 kg SOF(200mg)+RBV (N =)	< 17 kg SOF(150mg)+RBV (N =)	>= 17 kg SOF(200mg)+RBV (N =)

GT = genotype

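### SAP 8.1 gives one GS-331007 exposure ratio for 3 to <6-year-olds who receive two SOF doses, so the ratio can sit inside 50–200% while one dose lies outside

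*SAP*

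**What the plan says.** Protocol 3.1.1 sets the lead-in size: "Three cohorts of up to 10 subjects each will be sequentially enrolled". Within the third cohort, weight decides the dose: "Cohort 3 subjects weighing <17 kg will receive 150 mg SOF", and those at or above 17 kg receive 200 mg. Neither document sets a minimum number per weight band.

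Protocol 9.4 makes AUCtau of GS-331007 the primary comparison with adults: "The 90% confidence intervals will be constructed for the ratio of geometric means of each PK parameters". The equivalence boundary is 50% to 200%. The section then says: "The effect of age and SOF dose on PK (SOF and GS-331007) will be assessed". It gives no method or criterion for that. It also has an individual rule: an AUCtau below the 2.5th percentile of adult values may call for a dose adjustment.

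SAP 8.1 gives its purpose as confirming the dose for each age group. PK parameters are summarised by cohort, and those of GS-331007 "will be compared between each age group from this study and the SOF NDA patient population", with a geometric mean ratio and 90% CI. The 50–200% boundary is not repeated there, and no dose-effect analysis appears.

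SAP 3.2 provides, for the 3 to <6-year-olds, "additional selected efficacy and safety analyses performed according to baseline weight and HCV genotype" (Table 3-2). SAP 5.1, 5.2, 6.2.2 and 7.1.6 use that split for demographics, baseline characteristics, SVR12 outcomes and the adverse event overview. Section 8 does not.

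**The concern.** The primary objective of the Lead-in is to evaluate PK and confirm the dose (protocol 2). Protocol 1.5 proposes the two Cohort 3 doses from body-weight scaling, expects each to give exposures within the adult range, and relies on Lead-in data to check this. A single ratio over both doses cannot show whether each one does so. Deviations in opposite directions cancel, and a deviation in a minority of the children is diluted. If one band has no children, the ratio is still reported for the whole age group.

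At stake is the wording of the result: both doses could be reported as confirmed on evidence that describes only their mixture, or only one of them. The dose split exists in the SAP but is not applied to the analysis whose stated purpose is dose confirmation.

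**Working it through.** **Inputs.** Up to 10 children in Cohort 3 (protocol 3.1.1). Adult GS-331007 AUCtau: mean 7120, CV 30.7%, N = 1695 (protocol Table 1-2). Boundary 50–200% on a 90% CI (protocol 9.4). The split of the 10 children between doses is not given and is assumed below.

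**Formula.** Log SD = sqrt(ln(1 + 0.307²)) = 0.30. The 90% CI is the ratio divided and multiplied by exp(1.645 × SD × sqrt(1/n + 1/1695)).

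**Reproducing the plan's figures (Table 1-2).**
- Cohort 1, n = 10, ratio 129%: 110–151 (stated 110–152).
- Cohort 2, n = 12, ratio 89.2%: 77–103 (stated 76.8–104).

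The stated intervals imply a log SD of 0.31–0.32, so 0.32 is used as a check.

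**Pooled Cohort 3, n = 10.** The CI factor is exp(1.645 × 0.30 × sqrt(1/10 + 1/1695)) = 1.17. The pooled CI is therefore within the boundary for any observed ratio from about 58.5% to 171%.

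Illustration: 3 children on one dose, 7 on the other dose at 100%.

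| Ratio in the 3 children | Pooled ratio (90% CI) | Those 3 alone (90% CI) |
|---|---|---|
| 45% | exp(0.3 × ln 0.45) = 79% (67–92) | 45% (34–60) |
| 210% | exp(0.3 × ln 2.10) = 125% (107–146) | 210% (158–279) |

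Both pooled intervals are inside 50–200%. Neither interval for the 3 children alone is. With log SD 0.32 the factor is 1.18 and the pooled intervals become 67–93% and 106–148%. If the CI instead uses the larger within-cohort SD that mixing creates (0.49 and 0.47) and a t quantile on 9 df (1.833), the lower limit in the first case is about 59% and the upper limit in the second about 164%, still inside.

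**The individual rule.** Adult geometric mean = 7120 / sqrt(1 + 0.307²) = 6806. The 2.5th percentile = 6806 × exp(−1.96 × 0.30) ≈ 3780, or 56% of the geometric mean. A child on a dose with true ratio 45% falls below it with probability Φ(ln(0.555/0.45)/0.30) = 0.76. At least one of 3 does so with probability 1 − 0.24³ ≈ 0.99.

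**An empty band.** The weight distribution is not given. If 10%, 20% or 30% of enrolled children weigh under 17 kg (assumed), the chance that none of 10 is on 150 mg is 0.9¹⁰ = 35%, 0.8¹⁰ = 11% or 0.7¹⁰ = 3%.

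**Would a ratio per band be informative?** With the same boundary, a band whose true ratio is 100% gives a CI inside 50–200% with probability 0.49, 0.89, 0.98 or 0.997 for n = 1, 2, 3 or 4 (0.40, 0.84, 0.96 or 0.99 with log SD 0.32).

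**The case against.** The strongest reply has four parts.

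- **Under-exposure would rarely go unnoticed.** A reader might infer that a dose at 45% of adult exposure passes silently. The documents do not support that: the individual rule would very likely flag at least one of the three children. The rule is discretionary and works only on the low side, so it does nothing for high exposure or an empty band.
- **The decision is a review, not a mechanical gate.** A reader might infer that enrolment at both doses opens on one pooled number. Protocol 5.2.3 describes a review of intensive PK and safety results, and protocol 9.4 has PK parameters listed. In protocol 1.2.1.4 the Cohort 1 dose was judged appropriate although the GS-331007 Cmax interval (137–206%) crossed 200%; Cmax is secondary. SAP 8.1 governs the study report, not enrolment. This stands. The same section also shows the value of separating doses: when two Cohort 2 children received 400 mg, PK was evaluated with their exposure scaled to 200 mg and again without them.
- **The illustrations are extreme.** Under dose-proportional PK, 45% on 150 mg beside 100% on 200 mg needs lighter children to have 0.75/0.45 = 1.67 times the apparent clearance of heavier ones, against the weight–clearance relation used in protocol 1.5. The 210% case needs 0.75/2.10 = 0.36 times. The arithmetic shows what pooling can hide, not what is likely.
- **Other PK work is planned.** The dose-effect assessment in protocol 9.4 and the population PK report in SAP 8.2 may separate the doses. Neither has a stated per-dose criterion, and the first is absent from SAP 8.1.

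**Conclusion.** The point holds as a gap in the dose-confirmation analysis. For 3 to <6-year-olds, SAP 8.1 as written yields one ratio for two doses, and that ratio can meet the protocol boundary while one dose does not. With 3 of 10 children on the deviating dose, true ratios of 45% or 210% leave the pooled interval comfortably inside 50–200%. These figures rest on a log SD of 0.30, an assumed 3:7 split and the other dose at 100%. They change little at 0.32.

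Protection is partial on the low side. No stated rule protects against high exposure or a band without lead-in children. A reader might infer that the 150 mg dose will probably go untested. The documents do not support this, because they give no weight distribution; under the assumed shares the chance of no child on 150 mg runs from 35% down to 3%. Neither dose is questioned here.

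**What to change.** In SAP 8.1, for the 3 to <6-year-olds, keep the age-group ratio and add, for each of the two Table 3-2 weight/dose bands:

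- the number of children with evaluable intensive PK and their individual values;
- the geometric mean ratios to adults, with 90% CI, for AUCtau and Cmax of GS-331007.

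Read AUCtau against the boundary in protocol 9.4, and cite that boundary in SAP 8.1. Word the dose-confirmation statement per band. Where a band has too few lead-in children for an informative interval (the calculation above suggests fewer than about 3), say that support for its dose rests on scaling and population PK.

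The cost is SAP wording and one table, with wider intervals per band. It uses data already planned, so it remains possible even if Lead-in enrolment is complete. No lead-in quota, enrolment gate or dose change is proposed.
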